1 INTRODUCTION

1.1 STUDY DESIGN

The EFC16720 study is a 24-week, randomized, double-blind, placebo-controlled, parallel-group, multi-center study to evaluate the use of dupilumab in adults and adolescents (≥ 12 to < 18 years old) with primary acquired chronic inducible cold urticaria (ColdU) who remain symptomatic despite the use of H1-antihistamine treatment. The study is designed to test the hypothesis that dupilumab will increase the proportion of participants with a negative ice cube provocation test at Week 24 compared with placebo. A negative ice cube provocation test is defined as the absence of a confluent hive/wheal at the entire skin site of exposure after an ice cube provocation test.

The study consists of 3 periods:

- Screening period (2 to 4 weeks).
- Randomized IMP treatment period (24 weeks).
- Post IMP treatment period (12 weeks).

Chronic inducible ColdU signs and symptoms will be evaluated after the ice cube provocation test, by the Investigator (hives/wheals intensity) and participant (itch severity, skin pain, skin sensation). In addition, chronic inducible ColdU disease activity will be assessed daily by the participant using ColdUAS questionnaire in an e-diary where the participant will report his/her skin reactions (wheals and swelling), skin sensations (itching, burning, pain or feeling hot), if they have been in contact with cold temperatures that usually cause skin reactions, if they have avoided trigger exposure, and overall symptoms severity. The study will also assess the effect of dupilumab on urticaria control, participants' HRQoL and overall health status, proportion of patients with cold urticaria requiring emergency medical care visit or treatment with epinephrine and on reduction of rescue therapy.

The total anticipated number of participants randomized in the study is 78. This corresponds to approximately 39 participants who will be randomly assigned to each intervention arm:

- Dupilumab: 300 mg every q2w for adults; 200 mg q2w for adolescents ≥ 30 kg and < 60 kg at baseline or 300 mg q2w for adolescents ≥ 60 kg at baseline.
- Matched placebo.

At least 4 participants randomized in the study will be adolescents (≥ 12 to < 18 years old) who will be recruited in a few selected sites in selected countries. Randomization will be stratified by age (adolescent versus adult) and within adult group by country and background H1-antihistamine regular/daily use (Yes/No).

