2 SAMPLE SIZE DETERMINATION

Sample size is calculated based on the following assumptions:

1. The placebo group has █ participants with negative ice cube provocation test at Week 24 and the dupilumab group has █ participants with negative ice cube provocation test at Week 24.
2. There is a drop-out rate of 10% in both groups.
3. The statistical test is a Z test that is based on the difference of the 2 proportions with unpooled variance estimate and 2-sided 1% significance level.
4. Participants are equally randomized to the dupilumab group and the placebo group.

With these assumptions, 39 participants per group (78 participants in total) will provide 90% power to detect the difference of █ response rate in the dupilumab group and █ response rate in the placebo group. The sample size calculations were performed using nQuery+nTerim 4.0.

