4.3.3 Sensitivity analysis

The following sensitivity analyses will be performed targeting the same estimand as in the primary analysis to assess the impact of other missing data handling strategies. In the primary analysis, participants with missing ice cube provocation test data at Week 24 will be considered as having positive ice cube provocation tests.

Tipping point analysis

A tipping point analysis will be performed for the primary endpoint with imputed missing Week 24 values as follows:

- **Step 1.** With the complete data, fit a logistic regression model with the ice cube provocation test result (1: negative, 0: positive) at Week 24 as outcome and treatment group, region (combined countries), and background H1-antihistamine regular/daily use (Yes/No) as covariates.
- **Step 2.** Compute the probability of having negative ice cube provocation test for the participant with missing Week 24 value in placebo group from the fitted model but with the coefficient of the treatment group being added by a constant d . At the same time, compute the probability of having negative ice cube provocation test for the participant with missing Week 24 value in dupilumab group from the fitted model but with the coefficient of the treatment group being subtracted by a constant p .
- **Step 3.** With the probabilities computed in **Step 2**, impute the missing ice cube provocation results at Week 24 by generating binary random variables with the corresponding probabilities. Repeat this process to generate 40 imputed datasets.

- **Step 4.** Apply the Cochran-Mantel-Haenszel test stratified by region and background H1-antihistamine regular/daily use (Yes/No) for each imputed dataset. The results obtained from multiple imputed datasets will be combined to generate statistical inference, i.e. p-value and treatment difference between 2 treatment groups. Then use the SAS MIANALYZE procedure to generate statistical inferences of the odds ratios by combining results from the 40 analyses using Rubin's formula.

Step 2 to Step 4 will be repeated iteratively until the p-value for treatment effect of dupilumab compared to placebo estimated is >0.01 .

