4.4.1.2 Main analytical approach

The intercurrent event handling strategy for the key secondary endpoints is the treatment policy/composite approach.

This key secondary endpoints will be analyzed using an analysis of covariance (ANCOVA) model with baseline value of the endpoint, treatment group, region (combined countries), and background H1-antihistamine regular/daily use (Yes/No) as covariates, with intercurrent events and missing data being handled by a hybrid method of the worst-observation carried forward (WOCF) and multiple imputation. For participants who took highly influential prohibited medications and/or highly influential rescue medications (see [Table 4](#)), their data after the medication usage will be set to missing, and worst post-baseline value on or before the time of the medication usage will be used to impute missing Week 24 value (for participants whose post-baseline values are all missing, the baseline will be used to impute). Participants who discontinue the treatment prematurely are encouraged to follow the planned clinical visits. For participants who did not take the highly influential prohibited medications and/or highly influential rescue medications, all data collected after treatment discontinuation will be used in the analysis. For participants who discontinue study intervention due to lack of efficacy, all data collected after discontinuation will be used in the analysis, and a WOCF approach will be used to impute missing Week 24 value if needed (i.e., due to study discontinuation). For participants who discontinue study intervention not due to lack of efficacy, all data collected after discontinuation will be used in the analysis, and a multiple imputation approach will be used to impute missing Week 24 value if needed (i.e., due to study discontinuation). This multiple imputation will use all participants excluding participants who have taken the highly influential prohibited medications and/or highly influential rescue medications on or before Week 24 and excluding participants who discontinue due to lack of efficacy on or before Week 24. Each of the imputed complete data will be analyzed by fitting an analysis of covariance model as described above. Statistical inference obtained from all imputed data will be combined using Rubin's rule. Descriptive statistics including number of participants, mean, standard error, and least squares (LS) mean changes (and standard error) score will be provided. In addition, difference of the dupilumab group against placebo in LS means and the corresponding 95% confidence intervals (CI) will be provided along with the p-values.

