4.6 MULTIPLICITY ISSUES

To strongly control the family-wise type-I error rate for testing the primary and selected secondary endpoints, hierarchical testing procedure is used. The overall two-sided alpha is 0.01. The comparisons with placebo will be tested based on the hierarchical order below at 2-sided $\alpha = 0.01$.

Order of the testing hierarchy:

1. Proportion of participants with negative ice cube provocation test at Week 24.
2. Change from baseline in local wheal intensity at the provocation site at Week 24 using the wheal intensity Likert scale ranging from 0 to 5 (clinician evaluation).
3. Change from baseline in proportion of cold urticaria symptom free days at Week 24 (exposure-adjusted and measured by ColdUAS).
4. Change from baseline in local itch severity at the provocation site at Week 24 using the Peak Pruritus Numerical Rating Scale (NRS, score 0 to 10) (patient reported).
5. Change from baseline in health-related quality-of-life (HRQoL) as measured by Dermatology Life Quality Index (DLQI) in participants ≥ 16 years old.

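### SAP 4.4.1.2 leaves the degrees of freedom for pooling imputations unstated; under the classical rule, hierarchy tests 2 to 5 would run at about 1.2% against the stated 1%

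*SAP*

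**What the plan says.** SAP 4.6 sets the error rate: "The overall two-sided alpha is 0.01". It adds: "The comparisons with placebo will be tested based on the hierarchical order below at 2-sided" 0.01. The order is:

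1. negative ice cube test at Week 24
2. wheal intensity
3. symptom-free days
4. itch NRS
5. DLQI

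Item 1 is a Cochran-Mantel-Haenszel test in which a missing Week 24 result counts as positive, so it involves no multiple imputation (SAP 4.3.2). Items 2 and 3 are the key secondary endpoints of SAP 4.4.1. They are analysed by ANCOVA with "baseline value of the endpoint, treatment group, region (combined countries), and background H1-antihistamine regular/daily use (Yes/No) as covariates", after a mix of worst observation carried forward (WOCF) and multiple imputation. On pooling, SAP 4.4.1.2 says: "Statistical inference obtained from all imputed data will be combined using" Rubin's rule. SAP 4.4.2 applies the same procedure to itch and DLQI, so items 2 to 5 all depend on that sentence.

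For these four tests, neither document gives the degrees of freedom of the pooled statistic, the number of imputations or the software. The tipping-point analysis of the primary endpoint (SAP 4.3.3) is more specific. It uses 40 imputed datasets and says to "use the SAS MIANALYZE procedure to generate statistical inferences of the odds ratios".

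**The concern.** The name Rubin's rule fixes the pooled estimate and its variance, but not which reference t distribution is used. The classical choice takes the complete-data degrees of freedom as infinite. That does little harm in a large trial. Here, "The total anticipated number of participants randomized in the study is 78", and the statistic in each imputed dataset is a t on about 72 degrees of freedom. With few missing values the classical formula returns hundreds or thousands of degrees of freedom, so the test is close to a normal test on a t statistic.

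The error is larger in relative terms further out in the tail, and this trial tests at two-sided 0.01. The strong-control claim in SAP 4.6, and p-values that fall close to 0.01, would then depend on a setting the plan does not fix.

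**Working it through.** **Inputs**

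- Level: two-sided 0.01 at each of five ordered steps (SAP 4.6).
- N = 78, about 39 per arm (SAP 1.1 and 2).
- Region has three levels: Asia, Latin America and Western Countries (SAP 5.3).
- Number of imputations M and fraction of missing information λ for items 2 to 5: not given. Assumed ranges are M = 5 to 40 and λ = 0.02 to 0.30. The value 40 appears only in SAP 4.3.3. SAP 2 assumes: "There is a drop-out rate of 10% in both groups".

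**The plan's own figures.** The 0.01 is a chosen level. A fixed sequence with every step at 0.01 has a nominal family-wise error of 0.01. The 90% power statement cannot be recomputed because the response rates are blacked out. The total is attainable: 10% against 48%, for example, needs 35 evaluable per arm, and 35/0.90 = 38.9, so 39.

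**Complete-data degrees of freedom.** Intercept 1 + treatment 1 + baseline 1 + region 2 + antihistamine use 1 = 6 parameters, and 78 − 6 = 72.

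**Limiting case, infinite degrees of freedom**

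- Critical value used: 2.576. Value needed on 72 degrees of freedom: 2.646.
- Size: P(|t₇₂| > 2.576) = 0.01205. At N = 74 it is 0.0122, and at N = 70 it is 0.0123.
- Width of the 95% interval: 1.960/1.993 = 0.983, so about 1.7% too narrow.

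**Finite M**

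- Classical: ν_cl = (M − 1)/λ².
- Barnard-Rubin: 1/ν_BR = 1/ν_cl + 1/ν_obs, with ν_obs = (73/75) × 72 × (1 − λ).
- Approximate size: 2·P(t on ν_BR > 0.995 quantile of t on ν_cl).

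For M = 40 and λ = 0.05, ν_cl = 39/0.0025 = 15,600 and ν_obs = 0.9733 × 72 × 0.95 = 66.6, so ν_BR = 66.3.

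| M | λ | ν_cl | ν_BR | Approximate size with ν_cl |
|---|---|---|---|---|
| 40 | 0.05 | 15,600 | 66.3 | 0.0122 |
| 40 | 0.10 | 3,900 | 62.1 | 0.0124 |
| 40 | 0.20 | 975 | 53.0 | 0.0127 |
| 40 | 0.30 | 433 | 44.1 | 0.0131 |
| 5 | 0.10 | 400 | 54.5 | 0.0123 |
| 5 | 0.30 | 44 | 23.3 | 0.0130 |

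With M = 5 the classical degrees of freedom are no longer close to infinite, but the size is still above 0.012. Over the whole assumed range it runs from 0.0122 to 0.0131.

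**Simulation under the null.** N = 78, six parameters, normal outcomes, values missing completely at random, and an imputation model with the ANCOVA covariates. Each row has about 40,000 to 60,000 replicates (Monte Carlo SE 0.0004 to 0.0005).

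| Missing | M | Size, classical | Size, Barnard-Rubin |
|---|---|---|---|
| 5% | 40 | 0.0125 | 0.0103 |
| 10% | 40 | 0.0120 | 0.0098 |
| 20% | 40 | 0.0126 | 0.0098 |
| 30% | 40 | 0.0121 | 0.0093 |
| 10% | 5 | 0.0116 | 0.0096 |

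The classical rule gives about 0.012 and the small-sample rule about 0.010.

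**Family-wise error.** If the primary null is true, items 2 to 5 are reached only after a false rejection at item 1, which this issue does not touch. If the primary null is false and item 1 is nearly always passed, the first true null among items 2 to 5 is tested at about 0.012, and family-wise error can rise to about that value.

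**The case against.** The strongest objection is that the plan never says classical. Rubin's rule with small-sample degrees of freedom fits the same sentence, and the size is then about 0.010. A reader might infer that these tests will run at 1.2% as written, but the documents do not support that. A reader might also argue that the procedure named in SAP 4.3.3 settles the matter through its default. That procedure is named only for odds ratios in the tipping-point analysis, and neither document states its default. This objection stands, so the magnitude is conditional.

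Second, the simulation is not the planned procedure, because it leaves out WOCF. It also ignores that adults are randomised within country while the ANCOVA adjusts only for region, which pools Canada, the USA and Germany. Leaving out a prognostic stratification factor makes a test conservative. A complete-data simulation with the 2.576 critical value (40,000 replicates, SE 0.0005, country sizes and effects assumed) gave sizes of 0.0127, 0.0109, 0.0105 and 0.0088 when within-region country differences explained 0%, 3%, 5% and 10% of residual variance. A modest country effect could therefore cancel or reverse the excess. This also stands, although the country effects are assumptions and an accidental offset does not justify an unspecified reference distribution.

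Third, the effect is small, and the study is declared positive on the primary endpoint alone (protocol 9.4.1). That is correct, and it limits the severity.

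**Conclusion.** The point holds as an omission with a conditional consequence. SAP 4.4.1.2 names a pooling rule for four of the five hierarchy tests without its degrees of freedom or the number of imputations. In its textbook form, the rule gives slightly anti-conservative p-values: about 0.012 against 0.010 per test, an excess of some 0.2 percentage points or about 20% in relative terms, with 95% intervals about 1.7% too narrow. This rests on N = 78, six parameters, normal outcomes, data missing completely at random and no WOCF. It is not sensitive to M or λ over the ranges shown.

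A reader might conclude that strong control fails across the whole hierarchy. It does not: the primary test is unaffected, and family-wise error can approach 0.012 only when the primary null is false. No conclusion on the primary endpoint changes. Severity is minor.

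**What to change.** In SAP 4.4.1.2, state the number of imputations and say that Rubin's rule is applied with Barnard-Rubin small-sample degrees of freedom, using the residual degrees of freedom of each ANCOVA as the complete-data value: 72 at N = 78, and fewer for DLQI if the subset aged 16 or over with a baseline DLQI is smaller. SAP 4.4.2 refers back to this procedure, so itch and DLQI are covered by the same text.

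The cost is one sentence in the SAP and one setting in the analysis program, with no new data and no design change. P-values become slightly larger and intervals slightly wider. In the simulations above, this brings the size back to 0.0093 to 0.0103.

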
4.4.2 Supportive secondary endpoint(s)

The change from baseline endpoints:

- Change from baseline in urticaria control test (UCT 4-item) at Week 24
- Change from baseline in local wheal intensity at the provocation site at Week 12 using the wheal intensity Likert scale ranging from 0 to 5 (clinician evaluation)

- Change from baseline in local itch severity at the provocation site at Week 12 and Week 24 using the Peak Pruritus Numerical Rating Scale (NRS, score 0 to 10) (patient reported)
- Change from baseline in local skin burning sensation at the provocation site at Week 12 and Week 24 using the peak burning sensation NRS (patient reported)
- Change from baseline in local pain severity at the provocation site at Week 12 and Week 24 using the peak pain sensation NRS (patient reported)
- Change from baseline in cold urticaria signs and symptoms severity at Week 24 on cold exposure days as measured by ColdUAS
- Change from baseline in health-related quality of life (HRQoL) as measured by Dermatology Life Quality Index (DLQI) in participants ≥ 16 years old, and in Children's Dermatology Life Quality Index (CDLQI) in participants ≥ 12 to < 16 years old at Week 24
- Change from baseline in Cold Urticaria Quality of Life (ColdU-QoL) at Week 24

The Week 12 and Week 24 values will be analyzed separately and use the same procedure as the key secondary endpoint. The endpoint change from baseline in DLQI will be summarized and analyzed in participants ≥ 16 years old who completed the DLQI at baseline. The endpoint change from baseline in CDLQI will be summarized separately in participants ≥ 12 to < 16 years old using descriptive analysis only.

The proportion endpoints below will be analyzed like the primary endpoint.

- Proportion of well-controlled participants (UCT ≥ 12) at Week 24
- Proportion of participants with an improvement of ≥ 3 in UCT 4-item from baseline to Week 24
- Proportion of participants with negative ice cube provocation test at Week 12

The two endpoints below will be summarized using the count and percentage of participants.

[figure not shown]
- Proportion of participants receiving rescue therapy for primary acquired chronic induced ColdU during the planned treatment period
- Proportion of participants with cold exposure triggered urticaria requiring emergency medical care visit or treatment with epinephrine (at provocation test and/or at home)

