5.1 INCLUSION CRITERIA

Participants are eligible to be included in the study only if all of the following criteria apply:

Age

I 01. Participant must be ≥ 12 years to 80 years (or the minimum legal age for adolescents in the country of the investigational site) of age inclusive at the time of signing the informed consent. For those countries where local regulations do not permit enrollment of adolescents (≥ 12 years to <18 years of age), the recruitment will be restricted to those who are ≥ 18 years of age.

Type of participant and disease characteristics

I 02. Participants who have a diagnosis of primary acquired chronic inducible ColdU defined as recurrence of itchy wheals and/or angioedema due to cold for longer than 6 weeks prior to screening visit (Visit 1).

I 03. Participants with positive ice cube provocation test, ie, presenting at least a confluent hive/wheal on the exposed skin area, at the screening visit (Visit 1) and randomization visit (Visit 2).

I 04. Participants meeting at least 1 of the following criteria despite regular/daily or as needed use of H1-antihistamine:

- Urticaria Control Test (UCT) (4-item) <12 at the screening visit (Visit 1) and randomization visit (Visit 2)
- Within 6 months prior to the screening visit, documented medical history of cold exposure triggered anaphylaxis or oropharyngeal edema
- Within 6 months prior to the screening visit, documented medical history of cold exposure triggered urticaria requiring emergency medical care visit or treatment with epinephrine.

I 05. Participants who are using a study-defined H1-antihistamine regularly/daily or as needed for primary acquired chronic inducible ColdU (see [Section 6.1.2](#) for the list of antihistamines allowed for the study). Regular/daily use is defined as H1-antihistamine intake for at least 4 days per week for at least 1 month prior to screening visit (Visit 1).

Note: The participants who take H1-antihistamine regularly/daily should have the dose stable for at least 5 consecutive days prior to screening visit (Visit 1). The participants who

take H1-antihistamine as needed should not take H1-antihitamine for at least 5 consecutive days prior to screening visit (Visit 1).

Weight

I 06. Body weight \geq 30 kg.

Sex

I 07. Male or Female

Contraceptive use by women should be consistent with local regulations regarding the methods of contraception for those participating in clinical studies.

a) Female participants

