8.1.4 Urticaria control test (UCT) 4-item version

The UCT is a PRO questionnaire for assessing urticaria control. The questionnaire has been developed and validated with patients with CSU and CIndU (25). It is comprised of 4 items: severity of physical symptoms of urticaria (itch, hives and/or swelling); QoL impairment; frequency of treatment being not sufficient to control urticaria; overall urticarial control. Recall period is "last four weeks". Each item is rated on a 5-point Likert scale (scored with 0 to 4 points). Low scores indicate high disease activity and low disease control. The UCT total score is

calculated by adding all 4 individual item scores. Accordingly, the minimum and maximum UCT scores are 0 and 16, with a score of 16 for complete disease control (25).

The minimal important difference (MID) of the UCT is determined to be 3 (31).

Participants will complete the UCT as described in the SoA ([Section 1.3](#)).

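### The entry criteria permit baseline UCT scores of 14 to 16, which cannot rise by 3 points, yet the all-ITT analysis counts these participants as non-responders and so attenuates the UCT improvement endpoint

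*SAP*

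**What the plan says.** **Entry.** Protocol 5.1, criterion I 04, admits "Participants meeting at least 1 of the following criteria despite regular/daily or as needed use of H1-antihistamine". The first of the three alternatives is UCT below 12 at both the screening and the randomization visit. The other two are event histories within 6 months before screening: cold-triggered anaphylaxis or oropharyngeal edema, and cold-triggered urticaria that led to emergency care or epinephrine. Neither of these sets a UCT limit.

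**Scale.** Protocol 8.1.4 states that "the minimum and maximum UCT scores are 0 and 16", with higher scores meaning better control and a four-week recall. It gives the minimal important difference as 3 points.

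**Analysis.** SAP 4.4.2 lists three responder endpoints: UCT of at least 12 at Week 24, UCT improvement of at least 3 at Week 24, and a negative ice cube test at Week 12. Its instruction is "The proportion endpoints below will be analyzed like the primary endpoint". SAP 4.3.2 and SAP section 3 then give the ITT population (everyone randomized), a Cochran-Mantel-Haenszel test stratified by region and background H1-antihistamine use, and missing data counted as non-response. Baseline UCT is neither a stratum nor a restriction, and it is not among the subgroups in SAP 4.3.5, which in any case apply to the primary endpoint.

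The same SAP section does set a baseline condition for another endpoint: the DLQI change is analysed only in participants aged 16 or over who completed the DLQI at baseline.

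**The concern.** A participant who enters through event history with UCT 14, 15 or 16 would need a Week 24 score of 17, 18 or 19 to qualify as improved. The scale stops at 16, so the outcome is non-response whatever the treatment does. Adding such participants to both arms leaves the number of responders unchanged and enlarges both denominators. The two response rates fall in proportion and move closer together.

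This route into the trial is plausible. The qualifying event may be up to 6 months old, whereas the UCT looks back four weeks, and Protocol 3.1 says that symptoms fluctuate with trigger contact. A participant with a severe event some months ago and little recent exposure could score high.

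At stake is the size of the reported effect on an endpoint that serves the first-listed secondary objective, disease control. The continuous UCT change in the same section adjusts for baseline by ANCOVA; the responder version does not.

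**Working it through.** **1. The plan's own figure.** SAP section 2 states that "39 participants per group (78 participants in total) will provide 90% power to detect the difference", using a Z test with "unpooled variance estimate and 2-sided 1% significance level". It also assumes: "There is a drop-out rate of 10% in both groups". The two response rates are blacked out, so 39 can be checked only for consistency. The formula is

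n = [p1(1 − p1) + p2(1 − p2)] × [(z0.995 + z0.90)/(p2 − p1)]², with z0.995 + z0.90 = 2.576 + 1.282 = 3.857 (from unrounded values).

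For example, 15% v 55% gives (0.1275 + 0.2475) × (3.857/0.40)² = 34.9, so 35 evaluable, and 35/0.9 = 38.9, so 39. The pairs 10% v 48%, 25% v 67% and 30% v 72% also lead to 39. The figure is not in dispute. No calculation is given for the UCT endpoints.

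**2. Inputs for the UCT improvement endpoint.**
- 39 per arm, equal allocation (SAP section 2).
- Ceiling: 16 − 3 = 13, so baseline 13 or below can respond and 14 to 16 cannot (Protocol 8.1.4).
- f, the share with baseline 14 to 16: not in the documents. Assumed 5%, 10% and 20%.
- Response among those able to respond: not in the documents. Assumed 25% placebo, 50% dupilumab.
- Two-sided 5%, matching the 95% confidence intervals planned. The 1% level belongs to the hierarchy in SAP 4.6, which does not contain this endpoint.
- No allowance for drop-out.

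**3. Formulas.** The ITT rate in each arm is (1 − f)p, so the ITT difference is (1 − f)(p2 − p1). Power = Φ(|difference|/SE − 1.960), with SE = √{[p1(1 − p1) + p2(1 − p2)]/n}. For ITT, use the diluted rates and n = 39. For the restricted analysis, use the undiluted rates and n = 39(1 − f).

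**4. Worked case, f = 10%.**
- ITT: rates 22.5% and 45.0%; SE = √[(0.1744 + 0.2475)/39] = 0.1040; 0.225/0.1040 = 2.163; Φ(0.203) = 58%.
- Restricted: n = 35.1; SE = √[(0.1875 + 0.25)/35.1] = 0.1116; 0.25/0.1116 = 2.239; Φ(0.279) = 61%.

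| f | ITT rates | ITT difference (points) | ITT odds ratio | ITT power | Restricted n per arm | Restricted power |
|---|---|---|---|---|---|---|
| 0% | 25.0% v 50.0% | 25.0 | 3.00 | 66% | 39 | 66% |
| 5% | 23.75% v 47.5% | 23.75 | 2.90 | 62% | 37.05 | 63% |
| 10% | 22.5% v 45.0% | 22.5 | 2.82 | 58% | 35.1 | 61% |
| 20% | 20.0% v 40.0% | 20.0 | 2.67 | 51% | 31.2 | 56% |

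The restricted difference stays at 25 points and the odds ratio at 3.00 throughout. With other assumed rates, 30% v 60%, the pattern is the same: 71% v 75% at f = 10% (35 per arm restricted) and 63% v 70% at f = 20% (31 per arm).

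**5. The same test on UCT of at least 12.** Here a participant controlled at entry can still lose control. Let f now be the share with baseline UCT of 12 or more, and q the proportion of them still controlled at Week 24. The ITT rate is fq + (1 − f)p. With the same 25% v 50%:

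| q, dupilumab v placebo | f = 10%: difference, ITT power | f = 20%: difference, ITT power |
|---|---|---|
| 90% v 90% | 22.5 points, 54% | 20.0 points, 44% |
| 90% v 75% | 24.0 points, 60% | 23.0 points, 55% |
| 90% v 70% | 24.5 points, 62% | 24.0 points, 59% |

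Restricting to baseline UCT below 12 gives 61% and 56%. It gains power if retention is equal in the arms, is about neutral at 90% v 75%, and loses power at 90% v 70%.

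**The case against.** The strongest reply has four parts.

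- **The number affected is unknown.** This stands. The documents permit baseline UCT 14 to 16 but do not say that anyone has it. A reader might infer that the trial contains a material group of this kind; nothing in the documents shows that. The 35% to 70% with a history of systemic reactions (Protocol 2.3.1) is not limited to 6 months and says nothing about UCT, so it does not supply f.
- **ITT is the declared estimand population.** The all-ITT rate is a legitimate description of the enrolled population, and a restriction gives this endpoint its own denominator. It also thins a test already split by three regions and antihistamine use. This stands as a reason to keep the full-ITT result on display. It does not make certain non-responders informative about treatment.
- **The power gain is small, because restriction also cuts n.** This stands: 1 to 5 percentage points at f of 5% to 20% with 25% v 50%. The larger gain is a risk difference that is not scaled down.
- **The endpoint is supportive.** This stands. SAP 4.6 leaves it out of the hierarchy. The continuous UCT change is baseline-adjusted, and baseline UCT is summarised by intervention group (SAP 5.3).

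It is tempting to extend the point to UCT of at least 12, on the ground that response is already settled for anyone controlled at entry. The documents do not support that. Such participants can worsen, and confirmed highly influential medication or missing Week 24 data also turns them into non-responders. Keeping control on one arm and losing it on the other is treatment information, and the second table shows that excluding them can cost power.

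**Conclusion.** The point holds for UCT improvement of at least 3 and only there as a change to the main analysis. The ceiling is arithmetic. Participants with baseline 14 to 16 are non-responders by construction, and the ITT risk difference is (1 − f) times the difference among those able to respond. At an assumed 25% v 50%, 25 points becomes 23.75, 22.5 or 20 at f = 5%, 10% or 20%, and restriction raises power from 62% to 63%, 58% to 61% and 51% to 56%. These figures rest on assumed response rates and an assumed f; if no participant enters at 14 or above, nothing changes.

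A reader might take this as bias in favour of dupilumab or as inflation of the type I error. It is neither. Randomization spreads these participants over both arms by a baseline characteristic, so the effect is attenuation and some loss of power. The primary endpoint, the testing hierarchy and the conclusion on study success are unaffected. This is a cheap improvement to a supportive endpoint.

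**What to change.** In SAP 4.4.2, before database lock:

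- Analyse UCT improvement of at least 3 in ITT participants with baseline UCT of 13 or below. The subset is defined before treatment, so the randomized comparison is kept.
- Report the number excluded in each arm, and give the full-ITT analysis as supplementary.
- Keep ITT as the main analysis for UCT of at least 12 at Week 24. At most, add a prespecified supplementary analysis in participants with baseline UCT below 12.

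The cost is a few lines of SAP wording and one or two extra tables. The downside is a slightly smaller n, somewhat thinner strata and a separate denominator for this one supportive endpoint. Prespecifying the restriction avoids a post hoc choice if high baseline scores turn out to be common.
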